Parkview Institutional Review Board
[name]
[name]
Office: [contact] or [name]

TITLE: Treatment of Vitamin D deficiency with large bolus cholecalciferol in the outpatient setting

PROTOCOL VERSION DATE: 1/2/19

VERSION: 3

PRINCIPAL INVESTIGATOR (PI):

Name: [name], DO

Address: [name]

[contact]

KEY PERSONNEL:

Name: [name], DO

Role in project: co-investigator

Name: [name], DO

Role in project: co-investigator

Name: [name], DO; [name]

Role in project: faculty advisor/study coordinator

I. OBJECTIVES

The primary purpose of our study will be to evaluate the efficacy of large, single bolus vitamin D supplementation for the treatment of vitamin D deficiency when compared to standard treatment regimens. The null hypothesis will be that large single bolus administration of vitamin D will be non-inferior in efficacy of the standard vitamin D replacement. Secondary objectives will include evaluation of the duration of sufficient serum levels after the large bolus of cholecalciferol and evaluation of compliance with single dose regimens compared with standard daily regimens. We hypothesize that large bolus vitamin D replacement will have a duration of sufficient serum levels of at least one year.

II. BACKGROUND AND SIGNIFICANCE

Vitamin D deficiency has been recognized as a worldwide health concern for many years. Vitamin D is a fat-soluble steroid hormone with known effects on the absorption of calcium, magnesium and phosphorus from bone and the gastrointestinal tract, as well as other, less well understood effects on multiple body systems. Vitamin D deficiency is seen more in elderly patients, patients with autoimmune disorders (2), chronic kidney disease (3), chronic liver disease (4), hypertension (5), and malabsorptive conditions such as inflammatory bowel disease (6). Vitamin D deficiency is more common at far north and south latitudes and in climates with decreased sun exposure.

Vitamin D deficiency is associated with increased calcium resorption from bone leading to osteomalacia and increased risks of osteoporosis (7,8). Treatment of vitamin D deficiency has been

shown to slow progression of osteoporosis in elderly women. In recent years, vitamin D deficiency has been shown to be associated with other health conditions including cardiovascular disease (9), hypertension, type 2 diabetes mellitus (10), thyroid dysfunction, colon cancer, and neuropsychiatric disorders such as depression and dementia. These conditions are simply associated with vitamin D deficiency and there is a paucity of data regarding the effect of treatment of vitamin D deficiency on the overall disease state. Interestingly, vitamin D supplementation had been associated with a decrease in overall mortality (11)

In humans, vitamin D is predominantly obtained via exposure to sunlight. Solar ultraviolet B (UVB) radiation penetrates into the skin and starts the synthesis of vitamin D3 from pre-vitamin D. This is then hydroxylated to 25-hydroxyvitamin D in the liver. Serum 25-hydroxyvitamin D is the vitamin D level that is checked on routine laboratory testing because it is the best measure for total body stores. The 25-hydroxyvitamin D is hydroxylated again in the kidney to the biologically active form, 1,25-dihydroxyvitamin D (2). The biologically active form has a short half-life in plasma.

Pharmacologic preparations of vitamin D are available as both enteral and parenteral depot formulations. Cholecalciferol (vitamin D3) and ergocalciferol (vitamin D2) are the two calciferols available in the United States. Vitamin D2 is a plant-derived form while vitamin D3 is the form naturally produced in humans. When administered, both forms enter the metabolism cascade at the first hydroxylation step. Large bolus doses of ergocalciferol have been available in the United States for decades while large dose cholecalciferol became readily available in the last 15 years. There is limited data but some small studies have shown Vitamin D3 to be more effective for treatment in humans (12).

High dose Vitamin D therapy in children and adolescents, also known as Stoss therapy, was initiated in late 1930's Germany in the study of treatment and prevention of rickets (13). Since that time several studies have been performed to investigate Vitamin D supplementation in many different areas, patient populations and disease states. Current Endocrine Society guidelines define vitamin D deficiency at levels <20 ng/mL and insufficiency of Vitamin D at levels <30 ng/ml. Those guidelines recommend daily supplementation equivalent to 5,000-6,000 IU to achieve levels above this range (2). There are not guidelines regarding the frequency of checking Vitamin D levels while on treatment.

The significance of this research will aim to help guide treatment guidelines in terms of routine laboratory testing for follow-up, which will then potentially aid in guidance of when repeat dosing will occur. Upon review of the literature, many articles looked at serum levels immediately after large dose administration and with follow up as far as 9 months, but in the longer follow up studies laboratory testing from initial dose to last check was sparse. While many studies had short term follow up after initial dose, whether this was due to initial serum Vitamin D levels or dosage administered was not clearly defined. This study will aim to provide closer follow-up after a researched dose of 300,000IU that has been shown to have minimal adverse effects and multiple benefits beyond serum Vitamin D levels.

III. **PRELIMINARY STUDIES**

The pharmacodynamics of cholecalciferol allow for the potential of infrequent, large bolus administration. Once absorbed, cholecalciferol is either metabolized into 25(OH)-D or can be redistributed into fat. 25(OH)-D has a prolonged circulating half-life of approximately 2-3 weeks prior to being further hydroxylated in the kidney to the active metabolite (14). Cholecalciferol that is redistributed into fat is released slowly overtime to sustain circulating levels of 25(OH)-D for prolonged periods of time between dosing (13, 15, 16).

To this point, there has been inconclusive research on the efficacy of high dose vitamin D supplementation for vitamin D deficiency. Studies have shown that doses of 300,000IU are typically most efficacious for normalizing vitamin D levels while minimizing adverse effects (16). Dosage of 250,000IU or less have been ineffective for long-term improvement of vitamin D status (17, 18, 16).

Doses greater than 300,000IU have shown similar efficacy in raising serum vitamin D levels but increase the risk of adverse effects (19). No studies have identified a standard duration of efficacy for large bolus vitamin D supplementation.

Of the studies that were reviewed, none showed significant adverse effects related to hypervitaminosis D. This was even with cholecalciferol doses greater than 300,000IU (13, 15, 16). Two case series that evaluated patients with vitamin D toxicity in India showed toxicity resulting from repeated cholecalciferol administration totaling greater than 1,000,000IU over a minimum of three months. All case reports of hypervitaminosis D reviewed had a significantly higher dose of cholecalciferol than our proposed dose.

IV. RESEARCH STUDY DESIGN

- Study will be a prospective, unblinded, randomized controlled study.
- There will be two study arms:
 - Large-bolus group that will get one-time, 300,000IU cholecalciferol.
 - Standard treatment group that will take 5,000IU cholecalciferol daily.
- Participants will be randomized based on the order they join the study. *Randomizer.org* was used to create a randomly organized set of 20 including 10 ones (large bolus) and 10 twos (standard treatment).

	A	B	C	D
1	Research Randomizer Results:			
2	2 Sets of 10 No Numbers Per Set			
3	Range: From 1 to 2 -- No			
4	Set 1	Set 2		
5	2	2		
6	1	1		
7	2	1		
8	1	2		
9	2	1		
10	2	2		
11	1	1		
12	1	2		
13	1	1		
14	2	2		
15				

- | | | | |
|-----|----------|-----|----------|
| 1. | Bolus | 11. | Standard |
| 2. | Standard | 12. | Bolus |
| 3. | Bolus | 13. | Standard |
| 4. | Bolus | 14. | Standard |
| 5. | Standard | 15. | Bolus |
| 6. | Standard | 16. | Standard |
| 7. | Bolus | 17. | Bolus |
| 8. | Bolus | 18. | Standard |
| 9. | Bolus | 19. | Bolus |
| 10. | Standard | 20. | Standard |

We will repeat this organization for subsequent sets of 20 participants to maintain relatively equal groups as participants are added.

- We plan to enroll a total of 100 participants. We should be able to meet the goals of the study with 86 participants. Please see Appendix A for calculation of study size.
- We expect the study to last a total of 20 months:
 - 6 months for initial enrollment
 - 12 months for data gathering
 - 2 months for analysis and write up

V. ABOUT THE SUBJECTS

- We plan to enroll a total of 100 participants.
- We anticipate 86 participants will complete the study.
- The subject's population will include residents of southeastern Colorado. We will include men and women, age 18-75. All ethnic groups will be included. All participants will be seen at Parkview Adult Medicine for primary care.
- Inclusion criteria will include:
 1. 18-75 years old
 2. Serum 25(OH)D level <20ng/mL
 3. Patient of Parkview Adult Medicine Clinic
 4. Not currently on vitamin D supplementation >5,000IU daily.
 5. No ergocalciferol administration within the last week.
- Exclusion criteria will include:
 1. History of hypercalcemia or hyperparathyroidism due to risk of elevation of calcium levels with administration of vitamin D.
 2. History of chronic kidney disease with a baseline creatinine >1.1mg/dL as this can alter the metabolism of vitamin D.
 3. History of gastric absorptions abnormalities such as previous intestinal surgery, Celiac disease, or inflammatory bowel disease as this can alter the absorption of vitamin D.
 4. History of bone diseases such as Paget's disease or osteoporosis (on treatment) or granulomatous conditions as these can alter vitamin D metabolism and calcium levels.
 5. History of thyrotoxicosis as this can alter vitamin D metabolism.
 6. Subjects on anticonvulsants, barbiturates, steroids, or calcium supplementation >1200mg/day as these can increase risk of elevated calcium levels.
 7. Subjects with known malignancy as metabolism could be affected by both the malignancy and chemotherapy.
 8. Subjects who are pregnant or breastfeeding as vitamin D metabolism and needs are known to be altered during pregnancy.
 9. Patients who do not speak English at a conversational level as all communication with the investigators and the study paperwork will be in English.
 10. Inpatient hospitalization at the initiation of the study dosing as this study is specifically focusing on outpatient treatment. Participants found to have Vitamin D deficiency while hospitalized will be considered for inclusion after they are stabilized and discharged from the hospital.

VI. VULNERABLE POPULATIONS

- Educationally disadvantaged individuals will be considered for the study. The forms and questionnaires will be written in language to attempt to make them understandable to everyone, including educationally disadvantaged individuals.
- Economically disadvantaged individuals will be considered for the study. No monetary incentives will be provided for participation in the study to avoid coercion to participate.

VII. RECRUITMENT METHODS

- The study population will be recruited from patients of the Parkview Adult Medicine Clinic (PAMC) after routine Vitamin D testing.
- Pre-screening will be done by the providers caring for patients both outpatient at PAMC and inpatient at Parkview Medical Center. These providers are the ones ordering/initially getting the results of routine Vitamin D level testing. They will be the first to inquire about the patients participating in the study. If patients do express interest, their contact information will be shared with the investigators for formal enrollment and consent.
- Recruitment flyers will be hung in exam rooms at PAMC for participants in read and express interest to their providers. Recruitment flyer can be found in Appendix B.
- Participants will not be forced to check their vitamin D level for sole purpose of screening for study participation. Investigators will be honest regarding potential benefits and risks of participating in the study and will be forthcoming with answers to all questions from the participants.

List recruitment methods/materials and attach a copy of each:

1. Flyer to be hung in the Parkview Adult Medicine Clinic (Appendix B)

VIII. COMPENSATION

- The participants will not be compensated monetarily for participation in this study.

IX. CONSENT PROCESS

- All participants will be patients at the Parkview Adult Medicine Clinic. Providers will be notified of study and inclusion/exclusion criteria. When, through routine testing, patients are found to have vitamin D deficiency the provider ordering the test will initially inquire if their patients are interested in participation. Once participants indicate their interest, the clinic providers will provide the investigators with the name of the interested party. Investigators will then meet with the participant at the Parkview Adult Medicine Clinic to go through the formal consent.
- No change to the informed consent will be needed.
- All providers and investigators will be forthcoming with goals of the study and the idea that participation is entirely voluntary. Investigators will not approach patients that are not under their care in clinic without first being notified by the appropriate provider. No benefits will be provided to the providers for referring their patients to the study.
- Participants who do not speak English and would require a consent form translator will not be included in the study.

X. PROCESS TO DOCUMENT CONSENT IN WRITING

- After participants are pre-screened by and express interest in participation to their PCP, study investigators will reach out to schedule the initial study meeting. At this meeting, the participant will meet with one of the investigators to go through the written consent and sign. A copy of the signed consent will be given to the participant.

XI. **PROCEDURES**

- **Initial, pre-study encounter:**
 - Participants will have their 25(OH)-D level drawn for routine screening purposes outpatient or inpatient. The ordering provider/team will recognize level <20ng/dL as potential candidate for the study and inquire regarding interest for participation.
 - If individual expresses interest in participation, their provider will provide the investigators with the measured vitamin D level and the prospect's contact information.
- **Phone call #1:**
 - Investigator will contact prospective participant to schedule initial screening encounter.
 - Phone call should take no more than 2-5 minutes.
- **Encounter #1:**
 - Participant will meet with one (or more) investigator to go through consent. The participant will be given a signed copy of the consent.
 - The participant and investigator will go through the screening questionnaire (Appendix C) and collect routine vital signs (Appendix D).
 - The participant will go to the Parkview outpatient lab to have complete metabolic panel for screening of renal function and calcium levels.
 - Visit should take approximately 45 minutes total.

IF PARTICIPANT MEETS ALL INCLUSION CRITERIA AND NONE OF THE EXCLUSION CRITERIA, THEY WILL PROCEED TO THE NEXT STEPS:

- **Randomization:**
 - As noted above, participants will be randomized into either Group 1 (large-bolus cholecalciferol) or Group 2 (standard treatment) based on their enrollment position.
- **Study meds:**
 - Based on the randomization group, participants will have a prescription for the assigned therapy sent to the Pharmacy at Parkview. They will be instructed to pick up the medications and start the medications the next non-weekend morning (pick-up meds on Friday-Sunday then start on Monday. Other days, start on the following day).
 - Group 1 will take six 50,000IU cholecalciferol tablets one time.
 - Group 2 will take one 5,000IU cholecalciferol capsule daily.
- **Phone call #2:**

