Appendix A: Confidence interval and sample size calculations

For Confidence interval of 95%

- 85 participants (rounded to nearest integer)

For Power of 90%

- 58 participants

Assumptions:

- Acceptable error rate of 3 units
- Significant data meaning > 6 unit change from baseline
- Standard deviation on 6.7
- The latter 2 were taken from Premaor et al.

Calculation for Confidence interval:

$$n_i = 2 \left(\frac{Z\sigma}{E} \right)^2 :$$

N = sample size

Z = constant for desired confidence interval = 1.96

σ is the standard deviation of the outcome of interest = 6.7

E = acceptable margin of error = 3

This was then multiplied by 2 (for the treatment group vs control group) and then divided by .9 (assuming a 90% retention rate)

Calculation for Power:

$$n_i = 2 \left(\frac{Z_{1-\alpha/2} + Z_{1-\beta}}{ES} \right)^2$$

N = sample size

$Z_{1-\alpha/2}$ = constant for standard normal distribution of 1-alpha/2= 1.96

$Z_{1-\beta}$ = constant for standard normal distribution of 1-beta= 1.282 (if power of 90%)

$$ES = \frac{|\mu_1 - \mu_0|}{\sigma}$$

ES = Effect Size =

Numerator is the expected difference between populations (taken from 9 month difference of Premaor et al)

σ is the standard deviation of the outcome of interest = 6.7

This was then multiplied by 2 (for the treatment group vs control group) and then divided by .9 (assuming a 90% retention rate)

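### Non-inferiority is written as the null hypothesis with no margin, and Appendix A sizes the trial for other questions, so the error rates of the primary claim are undefined

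*Protocol*

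**What the plan says.** The primary purpose in Section I is to compare the efficacy of a single large bolus with standard replacement. The hypothesis reads: "The null hypothesis will be that large single bolus administration of vitamin D will be non-inferior in efficacy of the standard vitamin D replacement". No non-inferiority margin follows there or anywhere else in the protocol.

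Section IV refers to Appendix A for the study size and states: "We should be able to meet the goals of the study with 86 participants". Section V plans 100 enrolled and adds: "We anticipate 86 participants will complete the study".

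Appendix A contains two calculations, both with SD 6.7:

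- A confidence-interval calculation giving 85, with "E = acceptable margin of error = 3".
- A calculation headed "For Power of 90"%, giving 58. It is a two-sided formula whose effect size is described as follows: "Numerator is the expected difference between populations (taken from 9 month difference" in a cited study). No value is printed beside it. The only 6 in the appendix appears as "Significant data meaning > 6 unit change from baseline".

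Each per-arm figure is doubled and then "divided by .9 (assuming a 90% retention rate").

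**The concern.** A null hypothesis stands unless the data are strong enough to reject it. With non-inferiority as the null, a small or noisy trial favours the claim, and lack of evidence can pass for support. The usual arrangement puts the burden of proof on the bolus: the null is a deficit of at least the margin, and type I error is the chance of declaring non-inferiority when the deficit is that large. Without a margin, that probability has no value.

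The sample size has the same gap. A half-width of 3 describes precision, and the 58 is the size for detecting a difference. Neither shows whether the trial can rule out a deficit that matters. A nominal two-sided 5% level and 90% power are stated, but they belong to the difference test and not to the primary claim.

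**Working it through.** **Inputs.** From Appendix A: SD 6.7, z = 1.96, z = 1.282 for 90% power, half-width 3, retention 90%. From Section V: 86 completers, or 43 per arm under the 1:1 allocation of Section IV. Assumed here, because the protocol does not say: the margin (shown as a range), the true difference (0, then a bolus deficit of 1), and a decision by the lower limit of a two-sided 95% interval. The normal approximation is used throughout.

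**Appendix A reproduced.**

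- Confidence interval: 2 × (1.96 × 6.7 / 3)² = 38.32 per arm; × 2 / 0.9 = 85.16, stated as 85.
- Power, with 6 as the numerator: 2 × (3.242 × 6.7 / 6)² = 26.21 per arm; × 2 / 0.9 = 58.25, stated as 58.
- Solving the second formula for the numerator at a total of 58 gives 6.01. The value 6 is thus inferred. The printed 6 is labelled a change from baseline, whereas the formula needs a difference between groups.

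**Non-inferiority power.** SE = 6.7 × √(2/n), which is 1.445 at n = 43 per arm. Appendix A's 85 already includes dropout, so on its own basis the completers are 85 × 0.9 ≈ 77, about 38 per arm, and SE = 1.537. Power = Φ((margin − true deficit)/SE − 1.96).

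| Margin (units) | 43 per arm, no deficit | 38 per arm, no deficit | 43 per arm, deficit of 1 |
|---|---|---|---|
| 3 | 55% | 50% | 28% |
| 4 | 79% | 74% | 55% |
| 4.7 | 90% | 86% | 73% |
| 6 | 98.6% | 97% | 93% |

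With t quantiles at 43 per arm and no deficit, the column becomes 53.7%, 78.1%, 89.5% and 98.4%, so the approximation is adequate.

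**Smallest margin with 90% power at no true difference.** 3.2415 × SE = 4.68 at 43 per arm and 4.98 at 38. At 43 per arm this is 4.68 / 6.7 ≈ 0.70 SD, so it rises or falls in proportion to the SD.

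**Size for 90% power at a smaller margin.** 2 × (3.2415 × 6.7 / margin)² gives 105 per arm for a margin of 3 and 59 for 4. Enrolment at Section V's 86% completion is 210 / 0.86 = 245 and 118 / 0.86 = 138. At Appendix A's 90% retention it is 234 and 132.

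**Illustration of the reversed null.** Suppose a two-sided 5% test of zero difference were used and a non-significant result were read as non-inferiority. The protocol states no such rule. At 43 per arm, Φ(1.96 − deficit/1.445) gives a non-significant result 45% of the time at a true deficit of 3, 21% at 4 and 1.4% at 6.

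**The case against.** The strongest reply has four parts.

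- *The 58 is already a non-inferiority size.* The formula is algebraically that of a non-inferiority test with margin 6, true difference 0 and one-sided 2.5%. On that reading 43 per arm gives 98.6% power and little is lost. This is correct, but Appendix A says neither that 6 is a margin nor that the true difference is 0. It calls the numerator an expected difference.
- *The numerator is not missing.* Appendix A attributes the 6 and the SD to the same cited study as the numerator, and 6 reproduces 58. The natural reading is a correct input under an inconsistent label. That stands, and the repair on this point is to clarify the label.
- *Precision drives the size.* The 86 in Section IV tracks the 85 from the interval calculation, and a non-inferiority conclusion is read from a confidence interval. That is a legitimate way to size a trial. Without a margin, however, a half-width of 3 cannot be interpreted. If 3 were itself the margin, a half-width equal to the margin would give only 50% power at no true difference.
- *A statistical analysis plan may supply the margin.* It could, but the reversed null is stated in the protocol itself, and Section IV has already fixed the size by reference to Appendix A.

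It is also fair to say that the protocol gives no basis for preferring a margin of 3 or 4 over 6. The range shows how much turns on the choice and does not predict what the margin should be.

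**Conclusion.** The point holds and must be fixed, because it concerns the primary hypothesis. The null is the wrong way round, no margin is stated, and neither sample size calculation is tied to the stated objective. Appendix A's arithmetic is sound but answers different questions. The gap applies to the error rates of the non-inferiority claim only.

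Its practical size runs from negligible to serious. If the two unit thresholds printed in Appendix A were borrowed as margins, power at 43 per arm would be 55% for 3 and 98.6% for 6. The planned size gives 90% power only for margins of about 4.7 units or more, conditional on SD 6.7, 86 completers and no true difference.

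**What to change.** In Section I, name the efficacy measure and one visit for the primary comparison. If the measure is mean 25(OH)D, which would fit Appendix A's units, state H0: bolus minus standard ≤ −margin, and H1: > −margin. Section XI draws levels at one week and at 3, 6, 9 and 12 months. The 9-month source of the numerator is only a planning input and does not settle the visit. Justify the margin on clinical grounds, and conclude non-inferiority only if the lower limit of the two-sided 95% confidence interval lies above −margin.

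In Appendix A, replace the power line with the non-inferiority power at the planned size for that margin. Print the numerator if it is kept, and say whether the 6 is a between-group difference or a change from baseline. Align the Section IV statement about 86 participants with the result. Fix the margin before any comparative results are examined: the study is unblinded and Section XVIII has data reviewed at least monthly.

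The cost is rewording, with no extra participants required. The downside is that stated power falls below 90% if the margin is under about 4.7 units, and the trial may then end inconclusive. Keeping 90% power would mean enrolling 138 for a margin of 4 or 245 for a margin of 3 at 86% completion, against 100 planned.

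### The one-week ergocalciferol window is shorter than the protocol's own 25(OH)D half-life and tied to no event, and 25(OH)D is not repeated before dosing, so eligibility, baseline and week-1 change can be contaminated

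*Protocol*

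**What the plan says.** - **Eligibility (Protocol, Section V).** Entry requires "Serum 25(OH)D level <20ng/mL" and "No ergocalciferol administration within the last week". The second criterion names no reference event: it could be the routine draw, consent, randomization or the first dose. Criterion 4 separately allows ongoing vitamin D up to 5,000 IU daily.
- **Pharmacology (Sections II and III).** Section II says of ergocalciferol and cholecalciferol that "both forms enter the metabolism cascade at the first hydroxylation step". Section III states that "25(OH)-D has a prolonged circulating half-life of approximately 2-3 weeks", in a paragraph about cholecalciferol.
- **Source of the baseline (Section XI and Appendix D).** Before the study, "Participants will have their 25(OH)-D level drawn for routine screening purposes outpatient or inpatient". No maximum age is set for this result. Patients found deficient in hospital are considered only after discharge. Appendix D has one field for 25(OH)D, the prescreening value.
- **Next measurements (Section XI).** Encounter #1 lists a complete metabolic panel and no 25(OH)D. The next 25(OH)D is one week after starting study medication, followed by 3, 6, 9 and 12 months.
- **Screening form (Appendix C).** It asks whether the patient takes vitamin D now, how much and which type. It has no field for the date of the last ergocalciferol dose.

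**The concern.** One week is a third to a half of the half-life that the protocol itself gives for the outcome. A window that short does not clear a recent ergocalciferol effect, and no later step catches what is left.

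A clinician who sees a routine value below 20 ng/mL may give ergocalciferol before the study meeting. Once a little over a week has passed, criterion 5 is met. The patient is enrolled on the old value, and the next 25(OH)D is taken after study drug has started.

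Two things are at stake. The patient may no longer be below the entry threshold at the first study dose. The change from the recorded baseline to week 1 would also include a rise that study drug did not cause. Because Appendix C does not capture the last-dose date, criterion 5 cannot be verified from the form, and affected patients cannot be identified from it later.

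**Working it through.** The protocol states no carry-over figure to reproduce. Its only computed figures, the Appendix A sample sizes, do reproduce and do not bear on this point:

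- 2 × (1.96 × 6.7 / 3)² = 38.32 per arm; × 2 / 0.9 = 85.16 (stated 85)
- 2 × ((1.96 + 1.282) / (6 / 6.7))² = 26.21 per arm; × 2 / 0.9 = 58.25 (stated 58)

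**Inputs**

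- Shortest permitted gap from last ergocalciferol dose to first study dose: 1 week (Section V, taking the first dose as the anchor because none is stated).
- Half-life of 25(OH)D: 2 to 3 weeks (Section III). Using it for ergocalciferol-derived 25(OH)D is an assumption.
- Visits: 1 week, then 3, 6, 9 and 12 months after the first study dose (Section XI), taken as 1, 13, 26, 39 and 52 weeks.
- Rise in 25(OH)D from ergocalciferol: not in the documents; assumed 5, 10 or 15 ng/mL.

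**Step 1: window against half-life.** 1/3 = 0.33 and 1/2 = 0.50 of a half-life.

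**Step 2: fraction remaining.** First-order decay, residual = 0.5^(t / half-life), with t in weeks since the last ergocalciferol dose. This takes the rise as complete at t = 0 and ignores release from fat.

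| Time | t | Half-life 2 weeks | Half-life 3 weeks |
|---|---|---|---|
| First study dose | 1 | 70.7% | 79.4% |
| Week-1 visit | 2 | 50.0% | 63.0% |
| 3 months | 14 | 0.8% | 3.9% |
| 6 months | 27 | 0.01% | 0.2% |
| 9 months | 40 | 0.0001% | 0.01% |
| 12 months | 53 | under 0.0001% | 0.0005% |

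**Step 3: in ng/mL for one affected person** (residual × assumed rise; range over the two half-lives)

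| Assumed rise | At first study dose | Week-1 visit | 3 months |
|---|---|---|---|
| 5 | 3.5-4.0 | 2.5-3.1 | 0.04-0.20 |
| 10 | 7.1-7.9 | 5.0-6.3 | 0.08-0.39 |
| 15 | 10.6-11.9 | 7.5-9.4 | 0.12-0.59 |

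**Step 4: eligibility.** If the underlying level has not otherwise moved, a recorded value is out of range at dosing once it is at least 20 minus the residual. For a rise of 10 ng/mL that is 20 − 7.9 = 12.1 to 20 − 7.1 = 12.9 ng/mL or higher.

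**Step 5: arm mean.** The shift in an arm's week-1 mean is the individual residual times the share affected, which the documents do not give. With an assumed 10-50% affected and a 10 ng/mL rise, it runs from 0.10 × 5.0 = 0.5 to 0.50 × 6.3 = 3.15 ng/mL.

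**The case against.** Several objections narrow the point, and most of them stand.

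- **Direction.** A reader might infer that carry-over is always credited to study drug. That holds only if ergocalciferol was given after the routine draw. If it was given before, it is already in the recorded baseline, and its decay lowers later change from baseline.
- **Duration.** A reader might infer that the bolus's duration of sufficiency is inflated. On the stated half-life it is not: the residual is at most about 4% at 3 months and negligible at 9 and 12 months. Section III says of cholecalciferol that "Cholecalciferol that is redistributed into fat is released slowly overtime to sustain circulating levels of 25(OH)-D for prolonged periods of time between dosing". Similar storage of ergocalciferol could prolong carry-over, but no rate is given.
- **Between-arm comparison.** The same entry rule applies to both randomized arms. Carry-over adds noise, and chance imbalance is possible, but nothing systematically favours one arm.
- **Comparison with Appendix A.** Setting the residual at dosing against the 6-unit change or the 3-unit margin is not a fair yardstick. No 25(OH)D is drawn at dosing, the residual applies only to affected persons, and the expected difference in Appendix A comes from a 9-month result.
- **Toxicity.** Section XV places the greatest risk one week after the bolus, but it also puts symptoms typically above 150 ng/mL and calls the overall risk low. A residual of a few ng/mL does not show a meaningful added risk.
- **Other prior vitamin D.** Criterion 4 permits continuing supplementation with no washout, so criterion 5 is not the only source of prior exposure. That is true, but it does not repair the baseline.

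None of this answers the core gap: the window is shorter than the stated half-life, has no anchor, and no 25(OH)D is listed between a routine result of any age and the week-1 visit.

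**Conclusion.** The point holds in a limited form. A patient who receives ergocalciferol between the routine draw and entry can satisfy criterion 5 and be enrolled on an outdated value. At the shortest permitted gap, 71-79% of the rise would remain at the first study dose and 50-63% at the week-1 visit, where it would be read as study-drug change. For assumed rises of 5-15 ng/mL, that is 2.5-9.4 ng/mL at week 1 in an affected person.

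For these patients the consequence is confined to eligibility, the recorded baseline and the week-1 within-arm change. The documents do not support a claim of bias between arms, of inflated one-year duration or of added toxicity.

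The figures rest on applying the stated half-life to ergocalciferol-derived 25(OH)D, on simple first-order decay without fat release, and on an assumed rise. How many patients would be affected is unknown, although the presence of criterion 5 suggests the investigators expect some prior ergocalciferol use.

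**What to change.** 1. **Section V, criterion 5:** reconcile the window with the half-life stated in Section III, and anchor it to a named event. The investigators must choose the length; none is proposed here.
2. **Section XI and Appendix D:** require the qualifying and baseline 25(OH)D to be drawn after the last ergocalciferol dose. The simplest route is to add it to the blood draw already planned at Encounter #1, with its own field in Appendix D beside the prescreening value.
3. **Appendix C:** add the date of the last ergocalciferol dose.

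The cost is one added assay on a blood draw already planned and one or two form fields. Some candidates will no longer qualify.

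The repeat draw corrects eligibility and most of the week-1 error, but not everything. With a baseline taken about one week after the last ergocalciferol dose, the week-1 change is off by 50.0 − 70.7 = −20.7% to 63.0 − 79.4 = −16.4% of the rise, instead of +50% to +63%. At 3 months, however, change from that baseline would be lowered by 70.7 − 0.8 = 69.9% to 79.4 − 3.9 = 75.5% of the rise. This is why item 1 is needed as well as item 2, and why both 25(OH)D values should be kept.
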